### Exclusion Criteria:

- Breastfeeding women and pregnant women, or women of child bearing potential who are not using a medically accepted means of contraception (to include oral, injectable, or implant birth control, condom, diaphragm with spermicide, intrauterine device, tubal ligation, abstinence, or partner with vasectomy);
- Current, ongoing serious suicidal risk as assessed by evaluating investigator or by scoring 5 or more on the item-10 of the MADRS.
- Unstable medical illness as determined by the investigator;
- Patients with schizophrenia or schizoaffective disorders (current or past);
- Substance use disorder during the 3 months prior to screening; except for Cannabis and Alcohol use Disorders.
- Clinical evidence of untreated hypothyroidism;
- Patients with any evidence of clinically significant liver abnormalities, or any liver transaminase level > 1.5 x ULN at initial screening, or > 5 x ULN during treatment;
- Axis II personality disorders that are the primary purpose of treatment, or would interfere with a patient's safety or compliance, as determined by the investigator during open-ended psychiatric interview;
- Patients currently being treated for a respiratory disorder (including asthma or COPD);
- For participants over the age of 60, evidence of dementia as determined by the St. Luis University Mental Status Exam (SLUMS; participants with total scores less than or equal to 20 will be excluded and referred to their Primary Care Physician for follow-up/dementia evaluation);

Structured psychotherapy focused on treatment of PTSD is exclusionary unless the subject has had at least 8 weeks of treatment prior to starting the study medication;

[figure not shown]
- **8. Privacy:** All reports generated from the data obtained through this study will protect the confidentiality of the subjects who participate in this study. All subjects will be given a "wallet card" which identifies them as a study participant and lists the emergency contact numbers. If a subject shows clinical deterioration (worsening of PTSD symptoms), [name] will determine whether: 1) the subject can remain in the study, or; 2) a higher level of care (e.g. referral back to treating psychiatrist or referral to emergency or inpatient care) is needed.

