- A. Participants: Twenty patients with a current diagnosis of PTSD or sub-threshold PTSD between the ages of 18-75 will complete the treatment phase of the study. Subjects will initially be pre-screened by phone interview and a preliminary medical record review. Eligible subjects will then be invited for an in-office visit and will complete the written informed consent process. Subjects will be thoroughly screened for inclusion and exclusion criteria as described below.
- B. Discontinuation of subjects: Subjects may be discontinued from study treatment and assessments at any time. Specific reasons for discontinuing a subject from this study are:
  - Voluntary discontinuation by the subject, who is at any time free to discontinue his/her participation in the study without prejudice to further treatment;
  - Clinical deterioration: The following are objective criteria for clinical deterioration, (1) a 35% increase in CAPS scores at any time during the study, (2) Patients with a CGI-I score ≥ 6 at any post-baseline visit, and (3) the onset of active suicidality as assessed by the study investigator or by scoring 5 or more on the item-10 of MADRS;
  - Evidence of neutropenia (ANC ≤ 1500) or other intolerable adverse reaction, or unable to tolerate study drug;
  - Transaminase levels > 5x ULN;
  - Safety reasons as judged by the investigator;
  - Stopping birth control or positive pregnancy test;
  - Evidence of illicit drug abuse (except for cannabis) or problematic alcohol use during trial;
  - Non-compliance to protocol as judged by the investigator; Subjects who do not take between 75-125% of study medication for two consecutive visits are considered non-adherent and are withdrawn from the study medication.

A subject that prematurely discontinues (i.e. stops study medication or no longer wishes to participate) will always be asked about the reason(s) for discontinuation and the presence of any adverse events. If possible, they will be seen and assessed by the investigator. Adverse events will be followed up as medically necessary.

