#### **Data Analysis**

Descriptive statistics will be calculated prior to statistical analysis. Distributions of quantitative variables will be assessed for normality using normal probability plots and Kolmogorov-Smirnov statistics and transformations or non-parametric methods will be used as necessary. All statistical tests will be two-sided. Uncorrected alpha level of 0.05 will be used for testing the primary hypothesis. Pairwise post-hoc comparisons and tests of secondary outcome measures will be adjusted using Holm-Bonferroni procedure. All analyses will be intent-to-treat. We will using mixed effects regression models, with time effects for the primary outcome variable (CAPS). We do not expect significant moderating effects of alcohol use comorbidity but will assess the interaction between treatment and alcohol use comorbidity and perform follow-up tests as necessary. This approach will be applied to most secondary outcome measures as well. Mixed effects regression models use all available data on each subject, are flexible in modeling the correlation structure of the data and give unbiased results under missing at random

assumptions. In addition to testing the potential moderating effect of comorbid alcohol use described above, we will also perform exploratory analyses to the assess moderating effects of depression, medication status, substance abuse, age, and gender by adding these factors one at a time to the models above and testing interactions between each potential moderator and treatment group. Effects of intermittent missing data due to noncompliance with treatment schedule can also be assessed.

Table 1. Schedule of Study Events\*\*

	1 doie 1. Senedule of Study Events											
Visit	Screeni ng a	Baselin e	1	2&3	4	5,6,&7	8	9,10,11	12	month follow- up		
Day	0	0	7	14&21	28	35,42, & 49	56	63, 70, &77	84	114		
Informed Consent b	X											
Demographics	X											
SCID / MINI	X											
C-SSRS baseline	X											
MGH ATRQ	X											
ETI-SR, KLS, GPELS, CES	X											
M-MACE	X											
Psychiatric Evaluation	X											
BP, Pulse, Resp., Wt., Temp.	X	X	X	X	X	X	X	X	X			
ECG	X											
Physical Exam	X											
СВС	X				X		X		X			
СМР	X				LFTs		LF Ts		LFTs			
Serum Pregnancy (1)/ Urine Pregnancy (2)	X(1)	X (2)			X(2)		X( 2)		X(2)			
Urinalysis	X											
Inclusion/Exclusion	X											
CAPS	X	X °				X (visit 6 only)			X	X		
MADRS	X	X	X	X	X	X	X	X	X	X		
PCL, QIDS-SR, PSWQ, PSQI, SDS, SAFTEE		X	X	X	X	X	X	X	X	X		

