Protection Against Risks: All clinical raters have experience in clinical psychiatric assessment and will make every effort to implement protocol procedures in a sensitive and supportive manner. Research interviews will be interrupted if subjects become distressed or object to answering questions. Other measures to minimize risks include the careful assessment of each subject before the study, and close clinical scrutiny during all aspects of the study. Screening for suicide risk factors and suicidality is described in the research design.

Weekly contact is maintained throughout the clinical trial. A study staff member will call participants, during any week in which there is no clinic visits, to help ensure subject safety and protocol adherence.

We have included safety measures such as discontinuation of the study drug and transition to standard clinical treatment should subjects worsen to a sufficient degree. These precautions are likely to be highly effective in minimizing risks. Subjects may be hospitalized if they have a worsening of their symptoms, including becoming suicidal. In this case or if subjects discontinue study medication they will receive standard short-term clinical treatment as indicated.

Due to the potential of riluzole to cause elevations in serum aminotransferase levels, subjects will have liver function tests performed prior to initiating the trial and monthly for the duration of the study, or more frequently if clinically indicated. Patients with any evidence of clinically significant liver abnormalities or any liver transaminase level > 1.5 x ULN at baseline will be excluded from the study. Subjects will be discontinued from the study if any LFT measure rises above 5 x the ULN once treatment has been initiated. This is the recommendation in the PDR and is what has been used in previous studies. If treatment is terminated due to physical risks, subjects will be followed carefully until resolution of symptoms and treated with the follow up care described in the protocol.

Subjects will also be asked to report any cough, difficulty breathing or chills to the study staff in order to monitor for the possible emergence of interstitial lung disease or hypersensitivity pneumonitis. The study investigator, physician/APRN, and rater ask patients about any new symptoms at every visit.

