Suicidal Ideation and Imminent Harm: Despite treatment, people with PTSD may get worse. All communications about suicide and threats are taken seriously. It is important to assess the risk of suicide carefully when working with these individuals. Many subjects may admit to fleeting thoughts of death or briefly wishing for death; these thoughts need to be considered in context of the subject's overall history, along with a consideration of other risk factors for suicide. Study clinicians will assess patients at each visit for suicide risk and potential. Individuals at such risk will be treated appropriately, including options such as increased contact, more frequent clinical visits, or emergent psychiatric hospitalization. Subjects who score > 5 on the MADRS item 10 (suicide) at screening will be excluded from the study. In addition, a serious suicide or homicide risk, as assessed by evaluating clinician will be considered an exclusion criterion.

Throughout the study, any subject who scores  $\geq 5$  on the MADRS item number 10 will be discontinued from the study. Any subject with scores of  $\geq 6$  on the CGI-I will be discontinued from the study.

Subjects will be informed of any important discoveries made during this study, which may affect their condition or willingness to participate in this study by leaving a message (with subject permission) to contact the study team or by letter, if the subject cannot be reached by phone.

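### The MADRS item-10 cut-off for exclusion at screening is stated two ways, and the two rules disagree at a score of exactly 5

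*Combined protocol and SAP*

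**What the plan says.** Item 10 of the MADRS is used for two purposes: to decide entry and to decide discontinuation.

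**Entry.** The Exclusion Criteria in section 7 exclude current serious suicidal risk, established either by the evaluating investigator or "by scoring 5 or more on the item-10 of the MADRS". In section 12, under Suicidal Ideation and Imminent Harm, the rule reads: "Subjects who score > 5 on the MADRS item 10 (suicide) at screening will be excluded from the study". The following sentence adds a criterion that does not depend on the score: "a serious suicide or homicide risk, as assessed by evaluating clinician will be considered an exclusion criterion".

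**On study.** Section 11.B lists, among its criteria for clinical deterioration, "the onset of active suicidality as assessed by the study investigator or by scoring 5 or more on the item-10 of MADRS". The paragraph of section 12 after the screening rule applies throughout the study: any subject scoring ≥ 5 "on the MADRS item number 10 will be discontinued from the study".

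**Schedule.** Table 1 marks MADRS at screening, at baseline and at every later visit. The inclusion/exclusion check is marked at screening only. The screening column also carries the psychiatric evaluation and the entry "C-SSRS baseline".

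**The concern.** A numeric eligibility threshold should have one value. Here the formal list uses an inclusive cut-off and the dedicated suicide-risk text uses a strict one, for the same item at the same decision. Both are current text, and the protocol does not say which section prevails if they differ. A clinician who looks up the suicide rule in section 12 could reach a different screening decision from one who works from the list in section 7. The same enrolment could then be recorded as compliant or as a protocol deviation, depending on the page consulted.

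What is at stake is consistent application of an entry rule on suicide risk. No sample size, power, alpha or effect estimate depends on it.

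**Working it through.** There is no planned figure to reproduce. The check compares the stated rules score by score.

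**Inputs**

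- Rule A, section 7, Exclusion Criteria: exclude if score ≥ 5.
- Rule B, section 12, screening sentence: exclude if score > 5.
- Rule C, section 12, next paragraph, throughout the study: discontinue if score ≥ 5.
- Rule D, section 11.B: discontinue at 5 or more, worded as an onset of active suicidality.
- Assumption: the item is scored in whole numbers. The documents do not describe its scoring.

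**Comparison**

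| Item-10 score | Rule A (section 7) | Rule B (section 12, screening) | Same entry decision? | Rule C (section 12, on study) |
|---|---|---|---|---|
| 4 or lower | not excluded | not excluded | yes | not discontinued |
| 5 | excluded | not excluded | **no** | discontinued |
| 6 or higher | excluded | excluded | yes | discontinued |

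**Results**

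1. There are two score-based entry statements, one inclusive and one strict. They differ at one score only, 5.
2. Differing purposes do not explain the gap. The section 12 sentence is expressly about screening, and the on-study rule is given separately in the next paragraph.
3. Taken alone, the section 12 screening sentence leaves a subject at 5 eligible on score, while the next paragraph discontinues a subject at that score.
4. The two on-study statements, Rules C and D, use the same number.
5. Table 1 has two MADRS ratings before visit 1 (screening + baseline = 2), so an unchanged score of 5 would be seen again at baseline. Because the eligibility check is marked at screening only, the table does not say that the baseline rating reopens eligibility.
6. The documents give no count or expected proportion of subjects scoring 5, so the number affected cannot be estimated.

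**The case against.** **The symbol may be a reading artefact.** The point turns on one character. A greater-or-equal sign typed as an underlined > would lose its meaning if the underline were dropped when the PDF was read, and underlining of sub-headings in section 12 is captured unevenly. On the other side, the next paragraph of the same text keeps two ≥ signs, for item 10 and for the CGI-I, so such symbols were not lost in general. The documents alone cannot settle this. The objection stands as a reason to check the source page before amending anything.

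**The formal list already covers a score of 5.** The section 12 sentence names scores that are excluded; it does not declare a 5 eligible. Both sentences can be applied together, and together they exclude a 5. This stands and limits the consequence. It does not make the two statements agree, and no order of precedence is given.

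**Other safeguards exist.** Clinician-judged serious risk excludes under both section 7 and section 12, and the C-SSRS and a psychiatric evaluation are done at screening. This also stands, although the documents attach no exclusion cut-off to the C-SSRS.

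**Stronger readings that a reader might infer, and that the documents do not support:**

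- *That the protocol's cross-references steer staff away from the list.* Section 11.A says "Subjects will be thoroughly screened for inclusion and exclusion criteria as described below", and section 12 says "Screening for suicide risk factors and suicidality is described in the research design". Both can naturally refer to the screening procedures in section 11, which do include a psychiatric interview, the MADRS and the C-SSRS. They are not evidence of a further fault.
- *That section 11.B would necessarily remove a subject whose score stayed at 5.* It speaks of an onset under the heading of clinical deterioration, and whether an unchanged pre-treatment score is an onset is arguable. Only the section 12 rule that applies throughout the study plainly reaches that case.
- *That the on-study statements can be left out of the reconciliation because they agree with each other.* Whether they fit the screening rule depends on which cut-off the investigators settle on.

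**Conclusion.** The inconsistency holds as printed: section 7 excludes at 5 or more, and the section 12 screening sentence excludes only above 5. It affects one score value and is minor.

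A reader might conclude that the protocol as a whole admits subjects scoring 5. It does not: the formal list excludes them, and clinician judgement is a separate ground. A reader might also suspect an effect on the efficacy result. Nothing in the documents supports that, and the primary analysis is unaffected.

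The conclusion rests on two assumptions: that the > in section 12 is what the source page shows, and that the item is scored in whole numbers. If the source page shows ≥, the point falls away.

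**What to change.** 1. Check the source page of section 12, Suicidal Ideation and Imminent Harm, for a lost symbol in the screening sentence. If it reads ≥, no amendment is needed.
2. If the difference is real, reconcile that sentence with the Exclusion Criteria in section 7 so that both state the same screening cut-off. The choice of threshold belongs to the investigators.
3. Confirm that the chosen cut-off is consistent with the on-study item-10 rule in sections 11.B and 12, so that no score is both acceptable at entry and a ground for discontinuation without explanation.

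The cost is one check of the source and, if needed, a short wording amendment. No patients, visits or assessments are added.

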#### **Possible Benefits:**

Subjects may not receive any benefit from participating, though it may help patients in the future by giving important information about the study medication and PTSD. Subjects may benefit from initial screening procedures that will include careful examination of their physical status and psychiatric condition. In the event that clinical abnormalities are discovered, subjects will be informed of the finding and referred for appropriate care. Subjects' conditions may improve from taking the study drug. However, we cannot and do not guarantee or promise that they receive any benefits from participating in the study. Study personnel will offer a referral to treatment after completion of this study. The relative risks and inconveniences associated with participation in this study are balanced by the potential benefits to society, particularly patients suffering from PTSD.

#### 13. Data Safety Monitoring Plan:

The investigator's assessment of the overall risk for subjects participating in this study is moderate.

#### **Moderate Risk DSMP**

# 1. Personnel responsible for the safety review and its frequency:

The principal investigator, [name]., will be responsible for monitoring the data, assuring protocol compliance, and conducting the safety reviews at the specified frequency, which must be conducted at a minimum of every 6 months (including when reapproval of the protocol is sought). During the review process, the principal investigator (monitor) will evaluate whether the study should continue unchanged, require modification/amendment, continue or close to enrollment. Either the principal investigator or the IRB have the authority to stop or suspend the study or require modifications.

# 2. The risks associated with the current study are deemed moderate for the following reasons:

- 1. We do not view the risks associated with riluzole as minimal.
- 2. Given the established safety and validity of the use of riluzole, we do not view the proposed study as high risk.

Although we have assessed the proposed study as one of moderate risk, the potential exists for anticipated and/or unanticipated adverse events, serious or otherwise, to occur since it is not possible to predict with certainty the absolute risk in any given individual or in advance of first-hand experience with the proposed study methods.

Therefore, we provide a plan for monitoring the data and safety of the proposed study as follows:

#### 3. Attribution of Adverse Events:

Adverse events will be monitored for each subject participating in the study and attributed to the study procedures / design according to the following categories:

- a. Definite: Adverse event is clearly related to investigational procedures(s)/agent(s).
- b. Probable: Adverse event is likely related to investigational procedures(s)/agent(s).
- c. Possible: Adverse event may be related to investigational procedures(s)/agent(s).
- d. Unlikely: Adverse event is likely not to be related to the investigational procedures(s)/agent(s).
- e. Unrelated: Adverse event is clearly not related to investigational procedures(s)/agent(s).

#### 4. Plan for Grading Adverse Events:

The following scale will be used in grading the severity of adverse events noted during the study:

- 1 Mild adverse event
- 2. Moderate adverse event
- 3 Severe

# 5. Plan for Determining Seriousness of Adverse Events:

#### Serious Adverse Events:

In addition to grading the adverse event, adverse events are evaluated to determine whether they meet the criteria for a Serious Adverse Event (SAE). An adverse event is considered serious if it:

- 1. is life-threatening
- 2. results in in-patient hospitalization or prolongation of existing hospitalization
- 3. results in persistent or significant disability or incapacity
- 4. results in a congenital anomaly or birth defect OR
- 5. results in death
- 6. based upon appropriate medical judgment, may jeopardize the subject's health and may require medical or surgical intervention to prevent one of the other outcomes listed in this definition, or
- 7. adversely affects the risk/benefit ratio of the study

An adverse event may be graded as severe but still not meet the criteria for a Serious Adverse Event. Similarly, an adverse event may be graded as moderate but still meet the criteria for an SAE. It is important for the PI to consider the grade of the event as well as its "seriousness" when determining whether reporting to the IRBs is necessary.

# 6. Plan for reporting serious AND unanticipated AND related adverse events, anticipated adverse events occurring at a greater frequency than expected, and other unanticipated problems involving risks to subjects or others to the IRBs

The investigator will report the following types of adverse events to the IRB: a) serious AND unanticipated events; b) adverse events occurring with a greater frequency than expected; and c) other unanticipated problems involving risks to subjects or others.

These adverse events or unanticipated problems involving risks to subjects or others will be reported to the IRB within 5 business days of it becoming known to the investigator, using the appropriate forms.

# 7. Plan for reporting adverse events to co-investigators on the study, funding and regulatory agencies

For the current study, the following individuals, funding, and/or regulatory agencies will be notified:

• All Co-Investigators listed on the protocol.

The principal investigator, [name] M.D., will conduct a review of all adverse events upon completion of every study subject. The principal investigator will evaluate the frequency and severity of the adverse events and determine if modifications to the protocol or consent form are required.

**14. Informed consent**: A VA waiver of written informed consent and VA HIPAA authorization is requested for a pre-screening phone interview and medical record review. Following the phone screen, if an individual appears to meet enrollment criteria and is interested in participating, the subject is invited for a face-to-face interview and VA informed consent and HIPAA authorization is obtained by one of the project investigators. A release of information is obtained for review of any available historical and clinical data. A written authorization form is obtained from each subject, permitting the research team to use, create, or disclose the subject's PHI for research purposes. The nature of the project, procedures, relative risks and benefits, and alternatives to participation in the project are discussed with the individual. Following this discussion, the individual is given a copy of the consent form to review at their leisure, and any questions are answered.

If the individual is interested in the project, written informed consent is obtained, and medical and psychiatric screening procedures are undertaken to confirm eligibility. A copy of the consent form is provided to all participants. If the individual decides not to participate in this study, the decision not to participate does not affect eligibility to participate in future studies, to receive treatment at the VACHS or to receive treatment on a private basis from a referring clinician.

15. Confidentiality: Reports generated from this study will not contain any identifying information about the participants. Research records are coded only by a number, and are stored in locked cabinets. Research records will be stored with the Clinical Neuroscience Division at the VA. Consent forms, HIPAA forms, enrollment logs and release of information forms will be kept locked in a place separate from subject data collection forms. Subjects will be informed their name and social security number will appear on subject payment vouchers that will be sent to Fiscal Service and the Agent Cashier for approval and reimbursement. Subjects will also be informed that medical evaluations, including physicals, EKGs, and urine/blood tests will be administered through the hospital and will become part of their permanent record. Finally, subjects will be informed that a hard copy of the consent form will be placed in their paper record. An electronic progress note citing subjects' participation in this research study will be entered in their VA electronic medical record upon entry into and exit from, the study.

16. Location of Study: West Haven VACHS.

17. Payment to Subjects: Subjects will be paid \$15.00 per hour for their participation in the screening visit (up to \$75). During the clinical trial, subjects will be paid \$50 per visit. Subjects will also be paid \$50 for the one-month follow-up visit. At the discretion of the investigator, subjects may be reimbursed for additional costs including travel, parking, transportation, meals, or other expenses. Participants may receive a possible total of \$825.00 if they participate in all aspects of the study.

